# 6.13.1. Analysis of Adverse Events

## 6.13.1.1. Treatment Emergent Adverse Events

A treatment-emergent adverse event (TEAE) is defined as an event that first occurred or worsened in severity after baseline. The MedDRA Lowest Level Term (LLT) will be used in the treatmentemergent derivation. The maximum severity for each LLT during the baseline period including ongoing medical history will be used as baseline severity. For events with a missing severity during the baseline period, it will be treated as "mild" in severity for determining treatment-emergence. Events with a missing severity during the postbaseline period will be treated as "severe" and treatment-emergence will be determined by comparing to baseline severity.

For events occurring on the day of first taking study medication, the case report form (CRF)collected information (for example, treatment emergent flag, start time of study treatment and event) will be used to determine whether the event was pre- versus post-treatment if available. If the relevant information is not available, then the events will be counted as post-treatment.

The counts and percentages of participants with TEAEs will be summarized by treatment using MedDRA Preferred Term (PT) nested within System Organ Class (SOC). Statistical comparisons will be applied at both the SOC and PT levels. Events will be ordered by decreasing frequency within SOC. The SOC will be in alphabetical order. For events that are sex-specific, the denominator and computation of the percentage will include only participants from the given sex.

An overview of the number and percentage of participants who experienced a TEAE, serious adverse event (SAE), death, discontinued from study treatment or study due to an AE, relationship to study drug will be summarized by treatment.

The counts and percentages of patients with TEAEs by maximum severity will be summarized by treatment using MedDRA PT. For each participant and TEAE, the maximum severity for the MedDRA PT is the maximum postbaseline severity observed from all associated LLTs mapping to the MedDRA PT. The maximum severity will be determined based on the nonmissing severities. If all severities are missing for the defined postbaseline period of interest, it will show as missing in the table.

### 6.13.1.2. Common Adverse Events

The counts and percentages of participants with TEAEs, overall and common (common TEAEs occurred in  $\geq$ 5% of participants before rounding), will be summarized by treatment using MedDRA PT. Events will be ordered by decreasing frequency.

## 6.13.1.3. Deaths

A listing of all deaths during the study will be provided. The listing will include participant identification including the treatment, site number, date of death, age at the time of enrollment, sex, cause of death as reported by investigator, cause of death as adjudicated by CEC. etc.

## 6.13.1.4. Other Serious Adverse Events

The counts and percentages of participants who experienced a SAE (including deaths and SAEs temporally associated or preceding deaths) during the postbaseline period will be summarized by

treatment using MedDRA PT nested within SOC. Events will be ordered by decreasing frequency within SOC. The SOC will be in alphabetical order.

A listing of all SAEs will be provided. The listing will include treatment, participant identification including the site number, date of event, age at the time of enrollment, sex, MedDRA SOC and PT, Reported term, severity, outcome, relationship to study drug, time from first dose of study drug to the event, AE start date, AE end date, seriousness, action taken related to study treatment and event outcome.

## 6.13.1.5. Other Significant Adverse Events

The counts and percentages of participants who discontinued from study treatment or study due to an AE during the postbaseline period may be summarized by treatment group using MedDRA PT nested within SOC. Events will be ordered by decreasing frequency within SOC.

## 6.13.2. Patient Narratives

Patient narratives will be provided for all participants who experience any of the following "notable" events:

- death
- serious adverse event, or
- permanent discontinuation of study treatment due to AEs.
- Pregnancy
- Adjudication Confirmed Major Adverse Cardiovascular Events
- Adjudication Confirmed Pancreatitis

Patient narratives (patient level data and summary paragraph) will be provided for participants in the randomized population with at least 1 notable event.

## 6.13.3. Special Safety Topics

For adverse events of special interest (AESI) or special safety topics, the counts and percentages of participants will be summarized by treatment and PT with decreasing frequency. Individual participant level data may be presented. Displays with individual participant level data may be created using various formats, such as a customized listing and/or a customized graphical participant profile. Adverse events of special interest are defined in each section of special safety topics, where applicable.

## 6.13.3.1. Acute Gallbladder Disease

All events of TEAE biliary colic, cholecystitis, or other suspected events related to gallbladder disease will be summarized by treatment groups by PT with decreasing frequency. Detailed searching criteria can be found in Appendix 1.

## 6.13.3.2. Exocrine Pancreas Safety

## 6.13.3.2.1. Pancreatic Enzyme

Observed pancreatic enzyme data (p-amylase and lipase) will be summarized by treatment and nominal visit.

The counts and percentages of participants with maximum postbaseline pancreatic enzyme value exceeding the following thresholds will be provided by baseline pancreatic enzyme value ( $\leq$  upper limit of normal [ULN], > ULN), and postbaseline:  $\leq 1x$  ULN, (>1 to  $\leq 3$ ) x ULN, (>3 to  $\leq 5$ ) x ULN, (>5 to  $\leq 10$ ) x ULN, >10x ULN.

An MMRM analysis will be used to analyze each pancreatic enzyme with a log transformed (postbaseline measure/baseline measure) response variable and treatment, nominal visit, treatment-by-nominal visit interaction as fixed effects.

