Injection training with Autoinjector demonstration device ^k		X																

Visit ^a	1	2 ^b	3	4	5	6	7	8	9	10	11	12	13	14	15	99°	ED ^d	801e
Week of Treatment	-2	0	4	8	12	16	20	24	28	32	36	40	44	48	52	52		4 wks Post TxP
Allowable Deviation (days)f		±7	±7	±7	±7	±7	±7	±7	±3	±3	±7	±3	±7	±3	±7	±7		±7
Fasting (>8 hours) Visit ^a	X	X	X	X	X	X	X	X			X		X		X	X	X	X
Telephone Visit									X	X		X		X				
Dispense study drug		X	X	X	X	X	X	X			X		X					
Observe participant administer study drug ⁿ		X																
Participant returns study drugs and injection supplies			X	X	X	X	X	X			X		X		X		X	
Review study participant diary, including study drug compliance			X	X	X	X	X	X	X	X	X	X	X	X	X		X	
						Labo	oratory	Tests										
Serum pregnancy test ^o	X																	
Urine pregnancy test ^p		X			X			X			X		X		X	X	X	
Follicle-stimulating hormone ^q	X																	
Chemistry panel (include Cr for eGFR calculation ^s and glucose)	X	X			X			X			X		X		X		X	X
Lipid panel	X	X						X							X		X	X
Insulin		X			X			X			X		X		X		X	X
C-peptide		X			X			X			X		X		X		X	X
Free fatty acids	X	X						X							X		X	X
Urinary albumin/creatinine ratio	Xr							X							X		X	X
Cystatin-c	Xr							X							X		X	X

Visit ^a	1	2 ^b	3	4	5	6	7	8	9	10	11	12	13	14	15	99°	ED ^d	801e
Week of Treatment	-2	0	4	8	12	16	20	24	28	32	36	40	44	48	52	52		4 wks Post TxP
Allowable Deviation (days)f		±7	±7	±7	±7	±7	±7	±7	±3	±3	±7	±3	±7	±3	±7	±7		±7
Fasting (>8 hours) Visit ^a	X	X	X	X	X	X	X	X			X		X		X	X	X	X
Telephone Visit									X	X		X		X				
Calcitonin	Xr				X			X							X		X	X
Hematology	Xr				X			X							X		X	X
HbA1c	X	X			X			X			X		X		X		X	X
Pancreatic amylase, lipase	X	X			X			X							X		X	X
Thyroid stimulating hormone	Xr																	
Immunogenicity (includes PK sample) ^{t, u}		X	X		X			X			X				X		X	X
Mental Health Questionnaires																		
Patient Heath Questionnaire- 9 (PHQ-9) ^v	X	X			X			X			X		X		X	X	X	X
Columbia-Suicide Severity Rating Scale (C-SSRS) (Baseline/Screening Version) ^v	X																	
Columbia-Suicide Severity Rating Scale (C-SSRS) (Since Last Visit Version) ^v		X	X	X	X	X	X	X	X	X	X	X	X	X	X	X	X	X
Self-Harm Supplement Form ^{v,w}	X	X	X	X	X	X	X	X	X	X	X	X	X	X	X	X	X	X
Self-Harm Follow-up Form ^w	X	X	X	X	X	X	X	X	X	X	X	X	X	X	X	X	X	X
	PROs ^x																	
Short-Form-36 Health Survey (SF-36), version 2, acute form		X													X		X	

Visita	1	2 ^b	3	4	5	6	7	8	9	10	11	12	13	14	15	99°	ED ^d	801e

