10.3. Statistical Analyses

10.3.1. General Statistical Considerations

Statistical analysis of this study will be the responsibility of Lilly or its designee. Any change to the data analysis methods described in the protocol will require an amendment ONLY if it changes a principal feature of the protocol. Any other change to the data analysis methods described in the protocol, and the justification for making the change, will be described in the SAP or the clinical study report. Additional exploratory data analyses may be conducted as deemed appropriate.

Unless otherwise noted, all tests of treatment effects will be conducted at a 2-sided alpha level of 0.05, and the confidence interval will be calculated at 95%, 2-sided. In statistical summaries and analyses, data will be analyzed as randomized.

Unless specified otherwise, efficacy and safety will be assessed using the modified intention-to-treat (mITT) population, which consists of all randomized participants who are exposed to at least 1 dose of study drug. Baseline is defined as the last non-missing data collected at randomization (prior to first dosing of study drug). Unless specified otherwise, safety assessments will compare safety of tirzepatide doses with placebo irrespective of adherence to study drug. Thus, safety analysis will be conducted using safety analysis set (SS).

Summary statistics for continuous measures will include sample size, mean, SD, median, minimum, and maximum. The analysis model to make comparisons among treatment groups relative to continuous measurements assessed over time will be a mixed model for repeated measures (MMRM), with terms of treatment, visit, and treatment-by-visit interaction, stratification factors, and baseline measurement as a covariate. An unstructured covariance structure will model relationship of within-patient errors.

Kaplan-Meier method will be used for estimation of cumulative event-free survival rates over time, and cox proportional hazards regression analysis will be used to compare hazard rates among treatments.

Summary statistics for categorical measures (including categorized continuous measures) will include sample size, frequency, and percentages. Logistic regression will be used to examine the treatment difference in binary efficacy outcomes if there is a need to adjust for covariates. Otherwise, Fisher's exact test will be used to examine the treatment difference in categorical outcomes.

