Each participant will have measurements of p-amylase and lipase (assessed at the central laboratory) as shown on the Schedule of Activities (Section 2) to assess the effects of the investigational doses of tirzepatide on pancreatic enzyme levels. Serial measures of pancreatic enzymes have limited clinical value for predicting episodes of acute pancreatitis in asymptomatic participants (Nauck et al. 2017; Steinberg et al. 2017a, 2017b). Thus, further diagnostic follow-up of cases of asymptomatic pancreatic hyperenzynemia (lipase and/or pancreatic amylase ≥3x ULN) is not mandated, but may be performed based on the investigator's clinical judgment and assessment of the participant's overall clinical condition. Only cases of pancreatic hyperenzynemia that undergo additional diagnostic follow-up and/or are accompanied by symptoms suggestive of pancreatitis will be submitted for adjudication.

All suspected cases of acute or chronic pancreatitis will be adjudicated by an independent clinical endpoint committee. In addition, AEs of severe or serious abdominal pain of unknown etiology will also be submitted to the adjudication committee to assess for possible pancreatitis or other pancreatic disease. Relevant data from participants with acute or chronic pancreatitis and those with severe or serious abdominal pain will be entered into a specifically designed eCRF page. The adjudication committee representative will enter the results of adjudication in a corresponding eCRF page.

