# 6.3. Adjustments for Covariates

The study is stratified by sex (female, male) and presence of comorbidities (Y/N).

Unless otherwise specified, for efficacy related analyses at 52 weeks, sex, presence of comorbidities and corresponding baseline value will be used as a covariate.

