## 6.13. Safety Analyses

Unless specified otherwise, safety assessments will be based on the SS (Table GPIA.6.1). All events that occur between the first dose date of study drug and the end date of study participation will be included, regardless of the adherence to study drug.

The statistical assessment of homogeneity of the distribution of categorical safety responses between tirzepatide doses and placebo will be conducted using Fisher's exact test, unless specified otherwise.

For the selected continuous safety parameters, the mean change from baseline differences vs. placebo will be assessed via an MMRM using REML. Data from scheduled visits will be utilized for this analysis unless specified otherwise, the model for the analysis during 52 weeks treatment period will include sex, presence of comorbidities at randomization, treatment group, visit and treatment-by-visit interaction as fixed effects, and baseline value of the safety parameter as a covariate. To model the covariance structure within participants, the unstructured covariance matrix will be used. If this model fails to converge, the covariance structures specified in Section 6.12.1.1 will be tested in order until met convergence. If the data does not warrant the MMRM model, then ANCOVA model will be conducted.

For selected safety parameters, time-to-first-event analysis via the Cox-proportional hazards model may be conducted. Participants without the event will be censored at the end of study participation. For participants experiencing the event, the "time-to-first-event" will be the time (in days) from first dose to first occurrence of the event.

Where necessary, the rate of events will be analyzed using a generalized linear mixed-effects model assuming the number of events follow a negative binomial distribution and with treatment as a fixed effect. The logarithm of days during the active treatment period will be adjusted as an offset to account for possible unequal treatment duration of follow-up between participants.

Unless otherwise specified, all the analyses listed in this section will be conducted using SS in the postbaseline period: up to 52 weeks treatment period plus the safety follow-up (Visit 801, if applicable) for all randomized participants.

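### The p-amylase and lipase MMRM omits, without explanation, the baseline covariate and stratification factors of the general models; adding log baseline costs almost nothing and may narrow the intervals.

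*SAP*

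**What the plan says.** - **SAP 6.13.3.2.1 (Pancreatic Enzyme)** gives the enzyme MMRM a "log transformed (postbaseline measure/baseline measure) response variable and treatment, nominal visit, treatment-by-nominal visit interaction as fixed effects". It lists no baseline, sex or comorbidity term, and names no covariance structure or estimation method.
- **SAP 6.13 (Safety Analyses)** sets the default safety MMRM: "unless specified otherwise, the model for the analysis during 52 weeks treatment period will include sex, presence of comorbidities at randomization, treatment group, visit", then the treatment-by-visit interaction, "and baseline value of the safety parameter as a covariate". It does not say on which scale the baseline enters when the response is logged.
- **Protocol 10.3.1** describes the general MMRM for continuous measurements over time, "with terms of treatment, visit, and treatment-by-visit interaction, stratification factors, and baseline measurement as a covariate".
- **Protocol Appendix 6.1.2** says the enzymes are measured "to assess the effects of the investigational doses of tirzepatide on pancreatic enzyme levels".
- **Protocol Section 2 (Schedule of Activities)** marks the row "Pancreatic amylase, lipase" at Visits 1 and 2, then at Visits 5, 8 and 15 (Weeks 12, 24 and 52), early discontinuation and Visit 801.

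Neither document explains why the enzyme model is shorter than the two general ones.

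**The concern.** Read at face value, the enzyme model drops three terms that both general models carry: baseline, sex and presence of comorbidities. Another reading is possible. Section 6.13.3.2.1 is incomplete by itself, so a programmer must return to 6.13 for REML and the covariance structure, and nothing says whether the covariates come along.

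On the face-value reading, dividing by baseline subtracts log baseline with a coefficient of exactly 1 and does not estimate that coefficient. If the true slope is not 1, residual variance is larger than necessary and part of any chance baseline imbalance stays in the treatment contrast. This MMRM is the only model-based comparison that 6.13.3.2.1 provides for the effect of dose on enzyme levels. The tirzepatide/placebo ratios at Weeks 12, 24 and 52 could therefore have wider intervals than the collected data allow.

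**Working it through.** The plan states no power, standard error or sample size for this analysis, so there is no figure of its own to reproduce.

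**Inputs.** From the documents: 70 randomised per arm in three arms, and 25% dropout (70 × 0.75 = 52.5, taken as 52 per arm). Assumed, because the documents give neither: ρ, the correlation of log baseline with log postbaseline, and k = SD(log postbaseline)/SD(log baseline).

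**Formula.** Let X be log baseline with variance σ², and Y log postbaseline with variance k²σ².

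- Log ratio without baseline: Var(Y − X) = σ²(1 + k² − 2ρk).
- With log baseline as covariate: residual variance = k²σ²(1 − ρ²).
- Variance ratio R = (1 + k² − 2ρk) / [k²(1 − ρ²)] = 1 + (1 − ρk)² / [k²(1 − ρ²)].

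The second form shows that R is never below 1, and equals 1 only when the slope ρk is 1. The CI width ratio is √R.

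**Example.** For k = 1 and ρ = 0.7, R = (2 − 1.4)/(1 − 0.49) = 0.60/0.51 = 1.176, and √R = 1.085.

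**CI width without log baseline, relative to with it:**

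| k | ρ = 0.5 | ρ = 0.7 | ρ = 0.8 | ρ = 0.9 |
|---|---|---|---|---|
| 0.8 | 1.323 | 1.262 | 1.250 | 1.282 |
| 1.0 | 1.155 | 1.085 | 1.054 | 1.026 |
| 1.2 | 1.072 | 1.017 | 1.002 | 1.012 |

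At k = 1.25 and ρ = 0.8 the slope is 1. Then R = 0.5625/0.5625 = 1 and there is no gain.

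**Cost of the covariate.** The variance penalty is about 1 + 1/(N − 4). For N = 210 the SE factor is √(1 + 1/206) = 1.0024. For N = 156 (52 per arm) it is √(1 + 1/152) = 1.0033.

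**Simulation checks.**

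- Single visit, three arms, no true effect, 4000 runs: both estimators were unbiased (means within 0.004 of 0). At k = 1 and ρ = 0.5, 0.7, 0.8, 0.9, the SE ratio without versus with log baseline was 1.152, 1.083, 1.052, 1.024 at 70 per arm, and 1.150, 1.080, 1.051, 1.023 at 52 per arm. At k = 1.25 and ρ = 0.8 it was 0.998 and 0.997, which is the 0.2–0.3% cost.
- Three-visit unstructured MMRM, two arms of 70, about 25% random dropout, k = 1, 600 runs per setting: adding log baseline cut the model-based SE by about 12%, 7%, 5% and 2% at the same four ρ values. The formula gives 13.4%, 7.8%, 5.1% and 2.5% before the covariate's cost.

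**Chance imbalance.** At k = 1, a baseline difference of one standard error shifts the unadjusted contrast by √((1 − ρ)/2) of its own SE: 0.50, 0.39, 0.32 and 0.22 at the four ρ values.

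**Dropout related to baseline.** In an illustrative version of the three-visit simulation, higher baseline raised dropout in the active arm only. The model without baseline was biased by about 0.02 to 0.06 SD, and adding log baseline largely removed this. The dropout mechanism is invented for illustration, so this shows direction only.

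**The case against.** **The SAP permits the departure.** The default in 6.13 applies only where nothing else is specified, and 6.13.3.2.1 specifies its own response and terms. Where the SAP relies on a general safety model elsewhere (eGFR and UACR, vital signs, selected laboratory tests), it lists no terms, so an explicit list looks deliberate. This stands: the shorter model is an unexplained choice, not a contradiction. Nor is it a breach of the protocol, which leaves analysis details to the SAP and allows a change to be justified in the SAP or the study report. The log scale does not explain the choice, because UACR is also logged and takes the default.

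**Baseline is already in the ratio.** It is, but with its slope fixed at 1. Change score and covariance adjustment are both valid under randomisation; only the second estimates the slope, and the precision argument rests on that.

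**The size cannot be established.** This stands. The gain runs from nothing to an interval about a third wider, depending on two unreported quantities. The comparison is still lopsided, because the worst outcome of adding the covariate is a 0.2–0.3% larger SE. The benefit of adding sex and comorbidities has not been quantified and is expected to be small.

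**Nothing depends on it.** This also stands. The MMRM carries no hypothesis, margin or alpha. The protocol itself says serial enzymes predict pancreatitis poorly in asymptomatic participants, and the event of special interest is adjudicated pancreatitis. The SAP would allow a baseline-adjusted version as an additional analysis, but choosing covariates after unblinding is weaker than naming them now.

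**Conclusion.** The concern holds as a minor improvement. The enzyme MMRM omits terms that SAP 6.13 and Protocol 10.3.1 include, and no reason is given. The listed model remains valid under randomisation. If baseline and postbaseline SDs are equal on the log scale (k = 1) and ρ is 0.7 to 0.9, its intervals are about 3% to 8% wider than necessary, and about 15% wider at ρ = 0.5. The loss grows if postbaseline values are less variable than baseline, and disappears when ρk = 1. All these figures rest on assumed ρ and k. If the general covariates were meant to carry over, there is no precision loss from their absence, but the text should say so and name the scale of the baseline term. No primary or key secondary result, alpha allocation or sample size is affected.

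**What to change.** In SAP 6.13.3.2.1, keep the log-ratio response and add log(baseline enzyme) as a covariate, with sex and presence of comorbidities as fixed effects. Log baseline is the main source of any gain; the stratification factors are for consistency with the general models. State the log scale explicitly so that it matches the response. With log baseline in the model, the log ratio and log postbaseline give the same treatment contrasts, so the planned ratio presentation is unchanged.

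If the shorter model is intended, say so and give the reason.

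The cost is one line of SAP text. Both enzymes are already collected at Visits 1 and 2, and the stratification factors are known at randomisation.

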## 6.13.3.2.2. Pancreatitis Events

Summaries of adjudicated and investigator-reported pancreatic events will be provided by treatment. Detailed searching criteria can be found in Appendix 1.

Treatment emergent adjudicated pancreatitis will be considered as AESI. Listing of participants with adjudicated pancreatitis may be provided if deemed necessary.

## 6.13.3.3. Gastrointestinal Safety

## 6.13.3.3.1. Nausea, Vomiting, and Diarrhea

Summaries and analyses for incidence and severity of nausea, vomiting (including "vomiting" and "vomiting projectile"), diarrhea (including "diarrhea" and "diarrhoea"), and 3 events combined, will be provided by each treatment group.

Summary of the prevalence over time for nausea, vomiting, and diarrhea will also be presented.

Time to the onset of nausea, vomiting, and diarrhea will be plotted.

